Diabetes distress is commonly assessed via the *Diabetes Distress Scale*¹⁴ or the *Problem Areas in Diabetes Scale*.¹⁶ Research indicates both measures demonstrate the construct of DD is distinct from general anxiety, stress, and depression.^{13,17-19} Both the *Diabetes Distress Scale* and *Problem Areas in Diabetes* scales assess DD in several domains, and each DD domain addresses a separate aspect of the burden of T2D.^{14,20,21} The *Diabetes Distress Scale* measures DD in four domains (i.e., regimen, emotional, interpersonal, healthcare provider),¹⁴ and the *Problem Areas in Diabetes Scale* assesses DD using similar domains (i.e., emotional, diabetes management, treatment, and social support burden).^{10,22} The *Diabetes Distress Scale* and *Problem Areas in Diabetes Scale* have demonstrated content validity in measuring an individual's perception of the resources available, or not available, for self-management.^{13,19}

Diabetes distress is associated with more T2D complications, increased stress, being prescribed insulin by a healthcare provider, poor diet and exercise, inadequate support environments, and is more prevalent among women.^{10,19,23-26} Diabetes distress levels correlate with self-management behaviors such as monitoring one's diet, engaging with providers, and monitoring one's blood glucose.^{9,15,27-29} High to moderate levels of DD are related to poorer glucose regulation¹⁵, higher HbA1c²⁰, lower medication adherence³⁰, and poorer quality of life.³¹ Additionally, individuals with DD report diabetes-related physical burden, health care system distress, and distress with comorbid conditions.⁹ In this proposal, we will first examine the association between DD, the Veteran's engagement in self-management, and the Veteran's HbA1c.

[figure not shown]
Guiding Framework.

The self-directed learning (SDL) theory provides a useful lens for examining factors that influence DD. The self-directed learning theory posits that adults diagnose their learning needs, formulate goals, identify necessary resources, select applicable strategies, and evaluate their learning needs with or without the help of others.³² Three components are key to applying SDL: (1) *person*—characteristics such as life

experience, education, motivation; (2) process—learning style, technology skills; and (3) context—social, environmental, and physical context.³²

Design

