Potentially eligible patients will initially be identified via VA CDW/electronic health records data extract. (ICD-10 codes: E11.9, E11.8, and other inclusionary criteria detailed below, as well as the absence of any exclusionary diagnoses).

Inclusion and Exclusion Criteria

Veterans must meet **all** inclusion criteria

- Diagnosis of type 2 diabetes (ICD-10 codes: E11.9, E11.8)
- Documentation of HbA1c drawn within the past 180 days
- Able to speak and read English
- Be able to provide informed consent to participate in the study.

Veterans who meet **any** one of the exclusion criteria will be excluded.

- New diagnosis of T2D within the last 60 days
- Hospitalization for mental illness within the past 30 days
- Receiving active chemotherapy and/or radiation treatment
- Diagnosis for Metastatic Cancer
- Recent hospitalization within the past 60 days that would influence their diabetes medication regimen (e.g., myocardial infarction, cerebrovascular accident, coronary artery bypass grafting, etc.)
- Currently receiving Kidney Dialysis
- Limited hearing or speech difficulties that influence the Veteran's ability to complete the survey
- Dementia, delirium, or other cognition issues that influence the Veteran's ability to provide consent and complete the survey.

We will use the quantitative surveys to describe the prevalence of DD and the sociodemographic, psychosocial, and environmental factors of DD and DD domains. We will survey up to Veterans ($n=250$), and balance enrollment by HbA1c (<9 or ≥ 9) and medication (no insulin, insulin), to describe DD. Using the same population of enrolled participants we will conduct the cognitive interviews ($n=12-15$) to guide our decisions about retaining, deleting, modifying, or adding to the DDS as well as qualitative interviews with Veterans with T2D ($n=36$) to obtain perceptions of DD, self-management strategies and barriers, and intervention delivery strategy. We will balance enrollment by HbA1c, medication, and *Diabetes Distress Scale* score (low, moderate, high).

Subject Recruitment

For the purposes of screening, recruiting, and determining eligibility information will be obtained through written communication with the prospective participant and/or identifiable private information will be obtained by accessing medical records. Potential

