participants will be identified utilizing the VA's Information and Computing Infrastructure (VINCI) Corporate Data Warehouse (CDW) and/or local electronic health record (EHR). With approval of a HIPAA waiver, we will initially conduct a data pull with real Social Security Numbers (SSNs) from VINCI. In order to identify potential participants, we will complete computer-based screening using the VA Corporate Database Warehouse and our established inclusion/exclusion criteria. Based on protocol we will select the appropriate number of participants to be included in each letter batch and create the letters for each batch of potential participants. Multiple batches of letters will be sent until we reach our recruitment goal. An IRB approved letter along with study information documents will be sent to the potential participant informing them of the study and providing a phone contact for study staff.

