Each week eligible participants will be mailed introductory letters that provide basic information about the study and let patients know that a study team member will call them to ask whether they are interested in participating. The letter will also provide patients with a telephone number they may call to leave a message saying they are not interested in participating and do not want to receive a call from the study team. Between 5-7 days after the letter is sent, the research assistant (RA) will call Veterans who do not opt out to assess interest in participation. Veterans who do not opt out will be screened for eligibility. Participants contacted will next complete a brief telephone-based screening questionnaire to assess eligibility criteria that are not captured in DVAHCS electronic medical records. We will only ask a limited number of questions that are needed to determine study eligibility. The RA will conduct a verbal consent process with eligible Veterans. Participants will then be asked if they would like to complete the surveys at that time or another date and time. The informed consent process will include the option to collect and use the Veteran's health record data in analysis for current study and future studies and re-contact the participant for the qualitative interviews. The surveys will be completed by a study research assistant. After the Veteran completes the quantitative surveys, we will screen the Veteran for eligibility based upon the Veteran's HbA1c, medication use, and Diabetes Distress Scale score. Eligible Veterans will be invited to complete the semi-structured interviews.

Consent Process

We will request a waiver of written consent, waiver of consent documentation and waiver of HIPAA authorization from the IRB to conduct recruitment activities described above. Every effort will be made to talk via telephone with participants in privacy of their own home when completing the consent and questionnaires for data collection. Participants will be able to indicate to study staff if they are in a private environment or if they would like to be called at another time. This will ensure privacy and protect against embarrassment of sensitive survey questions and interview details.

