Survey—Detailed study design and sampling plan. We will recruit Veterans ($n = 200$) with T2D and who receive care at the Durham VA. We will conduct targeted recruitment to ensure equal numbers of well- and poorly-controlled Veterans. We will classify the Veterans into *well-controlled* (defined by HbA1c value < 9 during the past 180 days) and *poorly-controlled* (HbA1c value ≥ 9 during the past 180 days); our sampling strategy is guided by VA/DoD clinical practice guidelines.⁴⁷ Using EHR/CDW data, we will classify Veterans into *no insulin* (defined by taking only oral T2D medications and/or non-insulin injectable medications during the past 180 days) and *insulin* (defined by taking any insulin during the past 180 days; these Veterans may/may not also take oral T2D medication(s)). We are balancing enrollment because Veterans with different medication regimens may experience different challenges that influence DD.^{34,48} We will oversample women and younger Veterans to ensure we obtain diverse perspectives about DD. We will address sampling challenges as these challenges arise in order to ensure we obtain a diverse sample while aiming for the numbers shown in the Table.

Table. Sampling plan for surveys.

HbA1c	Medication		
	No Insulin	Insulin	Total

< 9	50	50	100
≥ 9	50	50	100
Total	100	100	200

Sample Size Considerations. Although our sample size of 200 Veterans with completed surveys is driven by practical considerations of feasibility, we will have a sufficient sample size

to test our specified hypotheses regarding differences in DD. With our sampling plan, we assume an equal distribution of 100 patients within each HbA1c level and with/without insulin use. Given a sample size of 200 Veterans, we will be able to estimate 95% confidence intervals for a mean difference in the *Diabetes Distress Scale* with precision equivalent to an effect size of 0.28. Additionally, with a type-I error of 5%, we will have 80% power to detect mean differences in DD of effect size magnitude 0.4 between groups. Note that our conclusions from these analyses will be based on defining a clinically meaningful difference, such as a decrease in DD, and relationships via estimates and confidence intervals, rather than by p-values.

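### Type 2 diabetes is defined by a closed list of two E11 codes, so Veterans coded only with other E11 codes are never contacted, and the restriction is not explained

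*Combined protocol and SAP*

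**What the plan says.** The protocol gives the diagnosis codes twice.

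- Under Selection of Subjects, the record extract is built on "ICD-10 codes: E11.9, E11.8, and other inclusionary criteria detailed below, as well as the absence of any exclusionary diagnoses".
- Under Inclusion and Exclusion Criteria, the first inclusion criterion is "Diagnosis of type 2 diabetes (ICD-10 codes: E11.9, E11.8". The rule above it is "Veterans must meet all inclusion criteria".

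Under Subject Recruitment, the criteria are applied before anyone is approached: "we will complete computer-based screening using the VA Corporate Database Warehouse and our established inclusion/exclusion criteria". Letters follow from that list. The later telephone step is a "brief telephone-based screening questionnaire to assess eligibility criteria that are not captured in DVAHCS electronic medical records". Sources of Materials gives the medical record or CDW as the source of the diagnosis.

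The population is described more broadly. The survey sampling plan, under Data Analysis and Statistical Considerations, recruits Veterans "with T2D and who receive care at the Durham VA". The Design section also describes a sample of Veterans in care at Durham and sets no limit by diagnosis code or complication status.

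On complications, Background and Significance says: "Diabetes distress is associated with more T2D complications".

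**The concern.** The sampling frame is narrower than the stated population, and no reason is given. A Veteran with type 2 diabetes whose record holds only E11 codes other than these two is dropped by the computer screen and never receives a letter. No analysis can repair this, because no data are collected on such Veterans.

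Three uses of the data depend on the frame.

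- The survey is meant to describe how common diabetes distress is and what goes with it (closing paragraph of Inclusion and Exclusion Criteria).
- The survey Analysis Plan uses the results to decide which Veterans a self-management intervention should target.
- The cognitive and qualitative interviews draw on the same population, so decisions about Diabetes Distress Scale items would not hear from the omitted Veterans either.

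The omission matters most if the omitted Veterans differ in distress. The protocol's own background gives one reason why they might: distress is associated with more complications. That bears on the frame only if the omitted codes tend to mark complications. The documents do not define the codes, so this link is an assumption.

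**Working it through.** **Step 1. Can a Veteran coded only with another E11 code enter the study?**

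| Step in the protocol | Effect |
|---|---|
| Record extract (Selection of Subjects) | Two codes, with no wildcard and no sign that they are examples |
| Inclusion criterion | The same two codes; all inclusion criteria required |
| Computer screening (Subject Recruitment) | Applied before letters are sent |
| Telephone screen (Subject Recruitment) | Covers only criteria not in the record; the diagnosis comes from the record |

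The answer is no. This holds whatever the individual codes mean.

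**Step 2. Who is not lost?** The criterion does not require E11.9 or E11.8 to be the only code, and it sets no look-back period, whereas HbA1c, comorbidities and medications are each tied to 180 days. As written, one of the two codes anywhere in the record is enough. The loss is confined to Veterans who have neither.

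**Step 3. Are the plan's own figures affected?** Inputs from Sample Size Considerations: 100 per group, type I error 5% (taken as two-sided), effect size 0.4.

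- Power = Φ(0.4/√(2/100) − 1.96) = Φ(2.828 − 1.960) = 0.807, against 80% stated.
- 95% half-width = 1.96 × √(2/100) = 0.277 SD, against 0.28 stated.

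Both figures reproduce. Changing the code list at the same sample size leaves them as they are.

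**Step 4. What could the omission do to a mean?** Let s be the share of otherwise eligible Veterans outside the frame, and d their mean Diabetes Distress Scale score minus that of Veterans inside it, in SD units. The full-population mean is the frame mean plus s × d, so the frame mean is too low by s × d. The documents give neither s nor d. The values below are assumptions that show the scale only.

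| s | d = 0.2 | d = 0.5 |
|---|---|---|
| 0% | 0 | 0 |
| 10% | 0.02 | 0.05 |
| 40% | 0.08 | 0.20 |

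If d is zero there is no shift, and if d is negative the sign reverses.

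**Step 5. What could it do to the two primary contrasts?** With group-specific values, the frame contrast differs from the full-population contrast by s₁d₁ − s₀d₀.

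- Equal loss and equal d in both groups: the shift is 0.
- Assumed loss of 40% in the HbA1c ≥ 9 group and 20% in the < 9 group: (0.40 − 0.20) × 0.2 = 0.04 SD, to (0.40 − 0.20) × 0.5 = 0.10 SD, toward zero. The upper value is 0.10/0.4 = 25% of the design effect.
- The same split reversed: 0.04 to 0.10 SD in the other direction.

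The documents do not say which case applies. The same holds for the insulin contrast.

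**The case against.** The strongest reply is that everything beyond the frame restriction itself rests on facts outside the documents. They do not say what the two codes or any other E11 code covers, how codes are distributed at Durham, or how distress varies with them. That stands, and it limits the point to a frame that is narrower than the stated population, with consequences of unknown size.

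Other parts of the reply also stand.

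- Co-coding at any time keeps a Veteran eligible, so the loss may be small.
- The survey fills quotas of 50 per HbA1c-by-insulin cell and oversamples women and younger Veterans. An unweighted overall mean would therefore not be a Durham population estimate even with a complete frame.
- The stated primary goal is the comparison by HbA1c and by insulin. For that comparison, a narrower frame may change only the population being described.

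A reader might go further in four ways that the documents do not support.

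- That complications drive distress. The background reports an association: "Diabetes distress is associated with more T2D complications, increased stress, being prescribed insulin by a healthcare provider".
- That current dialysis is the only exclusion touching complicated diabetes, so that the two codes must be doing the rest by accident. Recent hospitalisation affecting the diabetes regimen, such as for myocardial infarction or stroke, is also excluded.
- That mean distress is understated and both contrasts are pulled toward zero. Steps 4 and 5 show that this needs values the plan does not give.
- That the HbA1c ≥ 9 cells will be hard to fill. No pool size is given, and letters go out in batches until the target is met.

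None of this supplies a reason for the two-code list or reconciles it with the population named elsewhere.

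**Conclusion.** The point holds as a mismatch between frame and stated population. That part rests on the text alone: two codes in both places, all inclusion criteria required, no recovery step and no justification.

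That the sample may under-represent more distressed Veterans is conditional on the omitted codes marking complications. If they do, the prevalence description and the choice of intervention target are the results at risk. The number of Veterans affected, and the size and direction of any bias, including on the two primary contrasts, cannot be determined from the documents. The illustrative figures (0 to 0.20 SD on a mean; from none to 0.10 SD in either direction on a contrast) show scale under assumed inputs and are not estimates. Power and precision are not in question.

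The change is worth making because it costs little and the omission cannot be corrected once recruitment is complete.

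**What to change.** In both places, the extract sentence under Selection of Subjects and the first inclusion criterion, replace the two codes with any E11.x code. Leave every listed exclusion unchanged. The cost is one line in the CDW query, a wording amendment and a longer list to screen.

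If the two-code restriction is intended, state the reason, and limit the stated population and the prevalence claim to Veterans whose records carry one of those codes.

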Prior to beginning recruitment, the PI will meet with key personnel to review the protocol, the informed consent process, and the collection of questionnaires. Research study staff will demonstrate the essential steps in how to implement the protocol to ensure proper technique is communicated to participants. PI will ensure all study staff are up-to-date with required VA security and privacy training. PI will also ensure

research study data are no longer accessible to study personnel when they are no longer part of the research team.

Study Procedures

All participants will participate in the survey, there is no randomization or groups. After the consent process, Veterans will complete a battery of survey questions administered by the RA. These surveys will be collected in the study RedCAP survey. In anticipation of recruitment challenges, we will use methods: (1) flexible staffing of the PC and RA, to recruit and enroll Veterans who have varying work and life commitments; (2) clear language in the initial recruitment letter, to indicate the time commitment for the survey; (3) using a call schedule developed by the Durham COIN PCs, we will make three calls on three different days, at three different times, and leave two messages. We will offer Veterans the option of completing the surveys via telephone. However, if the Veteran prefers to complete the surveys in person, we will meet with these Veterans in conjunction with their scheduled medical appointment at Durham VA.

Variables/data collected in RedCAP survey		
Variable	Measure	Source
HbA1c	Most recent value in the past 180 days	EHR/CDW
Diabetes Distress	Diabetes Distress Scale.	PRO
Demographics	Age, sex, gender, race/ethnicity, etc.	EHR/CDW
Comorbidities	Current medical diagnoses during the past 180 days	EHR/CDW
Medications	Currently prescribed medications during the past 180 days	EHR/CDW
Symptom severity	Diabetes Symptom Checklist-R.	PRO
Chronic Illness Needs	Chronic Illness Resource Survey.	PRO
Depression	The Patient Health Questionnaire-2 (PHQ-2).	PRO
PTSD	Primary Care PTSD Screen for DSM-5.	PRO
Social Needs	Health Related Social Needs Survey.	PRO
Self-Efficacy	Diabetes Empowerment Scale-Short Form (DES-SF).	PRO
Self-Management Behaviors	Summary of Diabetes Self-Care Activities.	PRO
Stigma, shame	PROMIS Stigma Short Form	PRO

Pain and physical activity	PROMIS Pain Interference – (Short Form 6a)	PRO

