Analysis Plan. Standard descriptive statistics (e.g., mean, standard deviation, median, IQR, proportions, etc.) will be generated to characterize the *Diabetes Distress Scale* as well as the associated factors (e.g., psychosocial, sociodemographic) in the sample. In particular, we will examine the distribution of variables for sparsely populated categories or for deviations from normality. Descriptive statistics will be generated separately by HbA1c level and by insulin use. Rather than p-values, standardized differences will characterize differences between these sample subgroups.⁴⁹ The primary goal of the surveys is to examine differences in *Diabetes Distress Scale* score by HbA1c level (HbA1c < 9 and HbA1c ≥ 9) and by medication regimen (no insulin, insulin). We hypothesize that mean DD will be higher in: (1) Veterans with HbA1c ≥ 9 vs < 9; and (2) Veterans who use insulin vs those who do not. These hypotheses will be evaluated via separate multiple regression models with continuous *Diabetes Distress Scale* score as the outcome variable, and with the primary predictor being either an indicator for HbA1c ≥ 9 or an indicator for insulin use. A limited number of additional predictors will be included in the adjusted model, chosen *a priori* by the guiding framework and by evidence of imbalance as indicated by the standardized differences. As exploratory analyses, we will also examine the interaction of HbA1c level and insulin use upon *Diabetes Distress Scale* score. Descriptive statistics will be generated by these four subgroups, and statistical inference will be conducted via a two-way ANOVA model including the main effects and interaction. All analyses will be performed using SAS software (SAS Institute Inc., Cary, NC). These analyses will enable us to determine which population of Veterans we should target for a diabetes self-management intervention. For instance, if we identify that DD is highest in Veterans with HbA1c ≥ 9, who do not use insulin, who are younger, and are male, we will target those Veterans for a self-management intervention. Knowledge of the factors associated with DD will provide insight into potential modifiable and unmodifiable barriers to T2D self-management.

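### The insulin group is defined by any insulin in the past 180 days, while hypothesis 2 concerns Veterans who use insulin and distress is measured at the survey

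*Combined protocol and SAP*

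**What the plan says.** The survey sampling plan, under Data Analysis and Statistical Considerations, takes the medication groups from records: "Using EHR/CDW data, we will classify Veterans into" no insulin and insulin. The insulin group is "defined by taking any insulin during the past 180 days". The no-insulin group is "defined by taking only oral T2D medications and/or non-insulin injectable medications during the past 180 days". Neither a minimum duration of insulin nor use on the survey date is required. The reason given for balancing on medication is that "Veterans with different medication regimens may experience different challenges that influence DD".

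The survey Analysis Plan predicts higher mean distress under hypothesis 2, for "Veterans who use insulin vs those who do not". It tests this with "an indicator for insulin use" in a regression with "continuous *Diabetes Distress Scale* score as the outcome variable".

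The measures tables in Design and in Study Procedures describe the medication variable as "Currently prescribed medications during the past 180 days". Their notes say that record data are drawn at enrolment, before the survey. Subject Recruitment lets the Veteran take the survey in the same call or at a later date.

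**The concern.** The hypothesis and the reason for balancing are both about living with a regimen. The classification rule, read literally, is about having had insulin at some time in six months. A Veteran who stopped insulin four months before the survey meets the rule, although that Veteran no longer uses insulin when the DDS is answered.

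The insulin indicator is one of the two primary predictors in the survey. It also sets the quota cells, enters the exploratory two-way ANOVA, balances the sample of 36 for the qualitative interviews, and feeds the choice of whom a later intervention should target. If the indicator does not mean current use, each of these describes a somewhat different population from the one named.

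**Working it through.** **1. Does the text close the gap elsewhere?**

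- The medication variable in the measures tables can be read as current prescriptions or as a look-back, so two programmers could derive different indicators.
- Sources of Materials takes medications from records only. No listed survey measure is described as asking about current insulin use.
- The exclusion for a hospitalization that would influence the diabetes regimen covers 60 days. It does not reach days 61 to 180, nor insulin stopped as an outpatient.
- The survey Analysis Plan has no sensitivity analysis by current use.
- The no-insulin group must be free of insulin for the whole window, so any misclassification runs mainly one way, into the insulin group.

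**2. The plan's own figures.** Inputs from Sample Size Considerations: 100 per group, type-I error 5%, difference 0.4 SD. Sidedness is not stated. Two-sided is assumed because it reproduces the stated power; one-sided would give 88.2%.

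- Standard error of the difference = √(2/100) = 0.1414 SD.
- 95% CI half-width = 1.96 × 0.1414 = 0.277 (stated 0.28).
- Power = Φ(0.4/0.1414 − 1.96) = Φ(0.868) = 80.7% (stated 80%; noncentral t gives 80.4%).

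Both figures reproduce. The point is one of definition, not arithmetic.

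**3. Effect of former users in the insulin group.** Let m be their share, and let C, F and N be the mean DDS of current users, former users and non-users. The difference wanted is C − N. The difference observed is

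(1 − m)C + mF − N = (C − N) − m(C − F).

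The bias is −m(C − F), and the documents give neither m nor F. If F = C there is no bias. If F = N the difference shrinks to (1 − m)(C − N). If F exceeds C the difference is overstated.

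**4. The case F = N, starting from 0.40 SD** (assumed shares, common SD of 1):

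| m | Observed difference (SD) | Power = Φ(d/0.1414 − 1.96) | n per group for 80% |
|---|---|---|---|
| 2% | 0.4 × 0.98 = 0.392 | Φ(0.812) = 79.2% | 103 |
| 5% | 0.4 × 0.95 = 0.380 | Φ(0.727) = 76.6% | 109 |
| 10% | 0.4 × 0.90 = 0.360 | Φ(0.586) = 72.1% | 122 |
| 20% | 0.4 × 0.80 = 0.320 | Φ(0.303) = 61.9% | 154 |

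Allowing for the extra variance of a mixed group lowers these powers by less than one percentage point.

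**5. Precision under a current-use definition.** If the insulin cells are filled with current users, 100 against 100 is kept and power stays at 80.7%. If former users are instead left out and not replaced, the standard error is √(1/100 + 1/(100(1 − m))). Power at 0.4 SD is then 79.7%, 78.6% or 76.0% for m = 5%, 10% or 20%, with CI half-widths of 0.281, 0.285 and 0.294.

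**The case against.** The plan may already mean current use. The sampling plan goes on to say that insulin-group Veterans may or may not take oral drugs as well, so any insulin could mean any regimen that contains insulin. With the current-prescription wording in the measures tables, the 180 days could be only the width of the data extract. A record-based rule is also objective and reproducible, and it can be applied before letters are mailed. The background links distress to being prescribed insulin and says that distress may persist, so former users might resemble current users. Finally, the sample size was set by feasibility and conclusions are to rest on estimates and intervals, so power is a weak yardstick.

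Much of this stands. The number affected could be small, and the direction of bias is open. But a primary predictor that can be derived in two ways needs settling whichever was meant. Reporting estimates instead of p-values does not help when the estimate itself may answer a different question.

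Two stronger readings are tempting and not supported. A reader might infer that the insulin and HbA1c windows are misaligned. Both are 180 days; what is left open is the order of events inside the shared window. A Veteran whose HbA1c of 9 or more came before insulin was started is still a current user, and a current-use definition would not move that person. A reader might also infer that insulin given only during an admission counts. Nothing in the documents says so.

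**Conclusion.** The point holds as a mismatch between definition and hypothesis. The insulin rule does not require use at the survey, the measures tables do not resolve this, and no planned analysis would show whether it matters.

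A reader might go further and infer that hypothesis 2 is biased toward no difference, or that its power is well below 80%. The documents do not support that. The share of former users is not given, and shrinkage depends on former users having non-user distress. Under that assumption the loss runs from about 1 to 2 percentage points of power at 2% former users to about 18 or 19 at 20%. Under other assumptions there may be no bias, or bias the other way. This is an inexpensive improvement to one of two primary predictors, not a demonstrated failure of the analysis.

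**What to change.** - Reconcile the medication wording in the Design and Study Procedures tables with the group definitions in the survey sampling plan.
- Keep the 180-day record rule to pre-sort recruitment letters.
- Add one yes/no question on current insulin use to the research assistant's call, which already screens for items missing from the records. Confirm the answer at the survey if that falls on another date.
- Define the indicator for hypothesis 2 and for the two-way ANOVA as current use at the survey. Say explicitly that former users then fall among those who do not use insulin, as the hypothesis reads.
- Repeat the analysis under the 180-day rule as a sensitivity analysis, and describe former users (insulin within 180 days, none now) in a separate row.
- As a separate descriptive item, flag Veterans whose insulin started after the HbA1c that classified them, since the new definition does not address that ordering.

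The cost is one extra question, a changed derivation, and either slight imbalance in the quota cells or minor rebalancing of later letter batches.
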